**NCT04214080**

**23.03.2018**

## STUDY PROTOCOL

Scientific Background:	Trunk control of children with CP has been affected by spasticity, weakness in the trunk muscles, incoordination activation of trunk extensor and flexor muscles. Trunk stabilization exercises are an essential component of the mobility of distal part of body, including neck movements. Strengthening the deep neck flexor muscles and bridge exercise improves trunk control in children with CP. The positive effects of neck and trunk stabilization exercises on static and dynamic trunk balance, on upper limb and visuoperceptual function in CP have been mentioned in the literature.
Objectives:	According to literature there was a relationship between vocal functions and posture, active trunk movements has an important role in sound production and lastly trunk stabilization, balance and activity level components are in relationship with each other. Thus in this study, it was aimed to investigate the effects of neck and trunk stabilization exercises on communication, activities of daily living and quality of life in children with CP with oral motor problem.
Design:	The effects of structured neck and trunk stabilization exercises program giving together with feeding and oral-motor intervention strategies in children with Cerebral Palsy with oral motor problem: a randomized, single-blind, placebo controlled study. In this study, children were divided into study and control groups using a randomized numbers table. Structured oral motor rehabilitation and Neurodevelopmental therapy method-Bobath concept (NDT-B) approach was performed to all of the children who were in accordance with the inclusion criteria and approved by their families. In addition to the structured oral motor rehabilitation and NDT-B approach, Study group was received intensive structured neck and trunk stabilization exercises based on NDT-B principles.

Sponsor:	Marmara University, Istanbul, Turkey
Measured Parameters:	
 
-Gross motor functions,
 
-Daily communication performance,
 
-Speech production,
 
-The capacity to do the activities in daily life,
 
-The physical functions, psychosocial functions and school functionality independent of disease in children,
 
-Evaluation of trunk in sitting position.
 

Study Center:	Marmara University Pendik Education And Research Hospital, Istanbul, Turkey

All procedures performed in studies involving human participants were in accordance with the ethical standards of the institutional and/or national research committee and with the 1964 Helsinki declaration and its later amendments or comparable ethical standards. Ethical approval was obtained from the Marmara University Faculty of Medicine Clinical Research Ethics Committee protocol code 09.2018.278.

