**“Evaluation of The Effect of Neck and Trunk Stabilization Exercises on
Quality of Life and Communication in Children with Cerebral Palsy with
Oral Motor Problem”**

NCT04214080

03.12.2019

Statistical Analysis Plan

Descriptive statistics for continuous variables are expressed as mean (X), standard deviation (SD) values (Height, weight, body mass index (BMI), gender, etc); it is expressed as number (n) and percentage (%) for categorical variables.

In calculations, statistical significance level (α) was taken as 5% and values with $p < 0.05$ expressed statistical significance. "Statistical Package for Social Sciences" (SPSS 16) statistics program was used for calculations.

Non-parametric tests were applied since the continuous variables in the study were not normally distributed. Mann-Whitney U test was used to compare continuous variables according to Control and Study groups (Visual Analogue Scale, Viking Speech Scale, Communication Function Classification System, Katz scale, Sub-parameters of PedsQL). Wilcoxon test was used for intra groups comparisons (Visual Analogue Scale, Viking Speech Scale, Katz scale, Sub-parameters of PedsQL). In determining the relationship between categorical variables and groups, Chi-square test was performed (CP subtypes, Number of Medication, Types of Medications).

Spearman's Correlation Analysis was used to determine the relationship between groups of cases and other categorical and continuous variables (Visual Analogue Scale and Katz scale correlation analysis results with Communication Function Classification Systems).

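### The Design entry labels the trial placebo controlled, but the arms it describes are shared therapy with or without an added programme, and no placebo condition is described

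*Protocol*

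**What the plan says.** All of the relevant design text is in the Design entry of the protocol's synopsis table.

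- **Label.** The trial is "a randomized, single-blind, placebo controlled study". The same title-like sentence describes the neck and trunk "stabilization exercises program giving together with feeding and oral-motor intervention strategies".
- **Allocation.** The entry states that "children were divided into study and control groups using a randomized numbers table".
- **Therapy given to both arms.** For oral motor rehabilitation and NDT-B, it says the "approach was performed to all of the children who were in accordance with the inclusion criteria".
- **Therapy given to one arm.** "In addition to the structured oral motor rehabilitation and NDT-B approach", the Study "group was received intensive structured neck and trunk stabilization exercises based on NDT-B principles".

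The Objectives entry gives the aim as the effects of the neck and trunk exercises on communication, daily activities and quality of life. The rest of the protocol text is background, measured parameters, the study centre and ethics approval.

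The SAP refers to the comparator only by name: "Mann-Whitney U test was used to compare continuous variables according to Control and Study groups". It does not say what Control received.

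**The concern.** A reader who sees *placebo controlled* will assume that Control received something designed to balance the non-specific effects of the added programme: time with a therapist, attention, and the expectation of benefit. On that reading, a difference between groups after treatment can be attributed to what is specific to the exercises, which is how the Objectives entry frames the question.

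The arms as described do not support that reading. The Study group receives a further programme, described as intensive, on top of what everyone receives. The programme also rests on the same NDT-B principles as the shared therapy. A difference between groups could therefore come from the exercise content, from more therapy of a kind both arms already have, from extra contact, or from expectation. These all follow allocation, and the design as described estimates their combined effect. None of the methods in the SAP (Mann-Whitney, Wilcoxon, chi-square, Spearman) can separate them.

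The blinding statement does not settle the matter. The label says single-blind without naming the blinded party, and with no sham described it is unclear how children or families could have been unaware of their group.

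**Working it through.** There is no figure to reproduce. The check sets the label beside the arms and then looks for a placebo condition anywhere else in the two documents.

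**Step 1: the arms, from the Design entry.**

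| Component | Control | Study |
|---|---|---|
| Oral motor rehabilitation | yes | yes |
| NDT-B | yes | yes |
| Intensive neck and trunk programme | no mention | yes |
| Anything given to Control only | none described | – |

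Writing A for the shared therapy and B for the added programme, the contrast is A versus A + B. The described components number 2 for Control and 3 for Study, so the difference is 3 − 2 = 1, and that one is B.

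The title-like sentence also mentions feeding strategies, which the arm sentences do not. This does not change the structure. If feeding belongs to the shared therapy, the count is 3 versus 4 and the difference is still 1. If it went only to the Study group, the count is 2 versus 4. In neither case is there a component for Control alone.

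**Step 2: could the shared therapy be the placebo?** No. A placebo stands in for the tested treatment in the arm that does not receive it. A is given to both arms, so it cannot stand in for B in one of them.

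**Step 3: is a placebo described elsewhere?** Across the protocol text and the SAP, *placebo* occurs once, in the label itself. *Sham* and *attention* do not occur. The control group is named twice, once at allocation and once in the SAP's between-group tests, with no Control-specific condition at either place.

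**Step 4: can the imbalance be sized?** No. The words minute, hour, session, week and month do not occur in either document, so therapy time per arm is unknown. *Intensive* suggests more contact but gives no amount.

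**Step 5: which results are affected?** Only between-group comparisons after treatment; baseline comparisons are not.

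- The SAP lists five items for the Mann-Whitney test: Visual Analogue Scale, Viking Speech Scale, Communication Function Classification System, Katz scale and the PedsQL sub-parameters.
- Four of these five (all but the Communication Function Classification System) are also listed for the within-group Wilcoxon test, which implies that they were measured more than once.
- The SAP gives no time point for the Mann-Whitney tests, so how many of the five are post-treatment results cannot be determined.

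**The case against.** The best defence is that this is a wording slip which its own paragraph corrects. Anyone who reads the whole Design entry sees an add-on comparison, and the SAP, dated 03.12.2019 against 23.03.2018 for the protocol, does not repeat the label. An active-therapy control is legitimate. Neither document contains results, so no conclusion yet leans on the label. A difference in contact or expectation is possible but not shown. The text is also short and does not list everything: the unexplained mention of feeding shows that. Control may have received something that was not written down.

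Much of this stands. The add-on structure is partly disclosed, the randomised comparison is sound for the question it can answer, and the harm depends on how the result is worded. The missing detail on blinding and contact time would, taken alone, be a reporting gap.

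None of it removes the contradiction. Type of control is a basic design property, often taken from the label without the arm description, and here the label asserts something the described arms lack. The stated objective credits the exercises themselves, so the over-reading is a natural one. If an undescribed placebo condition did exist, the remedy is to describe it.

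**Conclusion.** The concern holds. The placebo-controlled label is not supported by the arms in the same entry or by anything else in the protocol text or SAP. What is described is a randomised comparison of shared therapy with and without an added programme.

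The consequence is limited to interpretation. A post-treatment difference supports a statement about adding the whole programme to the shared therapy. It does not support a statement about exercise content with contact and expectation held equal. The effect of this on the results cannot be quantified from the documents.

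The conclusion rests on the protocol text from the synopsis table onward and on the SAP. It does not assert that Control received nothing else, or that contact time in fact differed. Within those limits confidence is high, because the evidence is the text itself. The point should be corrected, but it does not invalidate the trial or its randomised analysis.

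**What to change.** Reconcile the label with the arms by one of two routes.

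1. If Control did receive a placebo or attention condition, describe it: what it was, who delivered it, and how much contact it involved.
2. If there was none, remove the placebo-controlled label from the protocol and every report, call the design a randomised add-on comparison against shared active therapy, and word conclusions as the effect of adding the programme to that therapy.

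Under either route, state who was blinded and report contact time per arm where it was recorded. It would also help to give the time point of each Mann-Whitney comparison, so that readers can see which results the narrower wording covers.

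The cost is editing, plus retrieval of contact-time records if they exist. If no placebo condition existed, the sponsor also accepts a less favourable design label and a narrower claim. Nothing changes in treatment, in the children studied or in the randomised analysis.

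### Does the SAP leave gross motor function and the trunk in sitting, both listed as measured in the protocol, without an analysis?

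*Protocol*

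**What the plan says.** The protocol, under Measured Parameters, lists six things to be measured. The first is "Gross motor functions" and the last is "Evaluation of trunk in sitting position". It names no instrument and no time point for any of the six.

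Under Objectives the protocol gives the aim: "it was aimed to investigate the effects of neck and trunk stabilization exercises on communication, activities of daily living and quality of life". The rationale there runs through the trunk: "active trunk movements has an important role in sound production and lastly trunk stabilization, balance and activity level components are in relationship". Under Design, what sets the arms apart is that the Study "group was received intensive structured neck and trunk stabilization exercises based on NDT-B principles".

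The third paragraph of the SAP states the between-group method in general terms, "Mann-Whitney U test was used to compare continuous variables according to Control and Study groups", followed by a bracketed list: "Visual Analogue Scale, Viking Speech Scale, Communication Function Classification System, Katz scale, Sub-parameters of PedsQL". For change within groups it says "Wilcoxon test was used for intra groups comparisons (Visual Analogue Scale, Viking Speech Scale, Katz scale, Sub-parameters of PedsQL". Chi-square is assigned to categorical variables by group, with cerebral palsy subtype and two medication variables in brackets. The fourth paragraph has Spearman correlations of the Visual Analogue Scale (VAS) and the Katz scale with the Communication Function Classification System (CFCS). No gross motor or trunk scale is named anywhere, and neither document says what the VAS rates.

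**The concern.** A reader who ticks off the protocol's list against the SAP finds two entries with nothing beside them. One of them, the trunk in sitting, is what the added exercises act on directly. If it was measured after treatment and is not analysed, the trial has no planned check on the first link of its own rationale. A null result on communication could then mean that the exercises did not change the trunk, or that they did and communication did not follow.

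There is also a reporting worry. A listed measure with no named test can be reported if it looks favourable and left out if it does not. The SAP is dated well after the protocol and describes the distribution of the data in the past tense, so it is natural to look for protection elsewhere in the documents and not find it. The VAS sharpens the point, because it enters three analyses with no stated construct.

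**Working it through.** The documents give no figure to reproduce on this point: no sample size, power, effect size or standard deviation. The check is a comparison of the two lists.

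**Step 1. Match by content.**

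| Protocol parameter | Nearest SAP variable | Basis |
|---|---|---|
| Gross motor function | none named | – |
| Daily communication | CFCS | construct visible in the name |
| Speech | Viking Speech Scale | construct visible in the name |
| Daily activities | Katz scale | inferred |
| Physical, psychosocial and school function | PedsQL sub-parameters | inferred |
| Trunk in sitting | none named | – |
| (no protocol entry) | VAS | construct not stated |

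Four of six (67%) have a counterpart, but only two of those four can be read from the scale's name. The SAP does not say what the Katz scale or PedsQL measures either. PedsQL cannot stand in for gross motor function, because the protocol lists physical function as a separate entry.

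**Step 2. Size of the gap.** It depends on what the VAS rates:
- neither parameter: 2/6 = 33% without a named test;
- one of them: 1/6 = 17%;
- both: 0/6, and only a label is missing.

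CFCS is in the Mann-Whitney list but absent from the Wilcoxon list. That fits a classification recorded once, in which case the VAS may be a communication rating. The documents do not settle this.

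**Step 3. Do the SAP's rules reach the two parameters?** The Mann-Whitney sentence covers continuous variables by group, and the Chi-square sentence covers categorical variables by group. The SAP already places a classification system under the first rule, so a motor or trunk score would fit there without strain. Nothing in the SAP excludes either parameter. The descriptive list ends in an open-ended abbreviation and the test lists do not. That favours reading the test lists as complete but does not prove it.

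**Step 4. Dates.** From 23.03.2018 to 23.03.2019 is 365 days, and from there to 03.12.2019 is 255, so the SAP follows the protocol by 620 days. No enrolment or completion dates are given. The 2018 protocol is also written in the past tense, so tense says little about when data were seen.

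**Step 5. What naming the tests would cost.** With k independent tests at 0.05, the chance of at least one false positive is 1 − 0.95^k. The Mann-Whitney list has four single scales plus the PedsQL sub-parameters, whose number is not stated. Assuming 3, k = 7:
- as listed: 1 − 0.95^7 = 30.2%;
- one test added: 1 − 0.95^8 = 33.7%;
- two added: 1 − 0.95^9 = 37.0%.

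For 2 to 5 sub-parameters the rise is 3.2 to 3.7 points for one added test and 6.1 to 7.2 points for two. Correlated outcomes would make it smaller. The cost is modest and does not decide the matter.

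**The case for a change.** The best case for a change is that the trunk is the direct target of the treatment, that the protocol says it was measured, and that the remedy is a few words and at most two secondary comparisons. The bracketed test lists look complete. An instrument used in three analyses ought to have a stated construct. Naming the two measures would give a reader something to hold the report against.

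Part of this stands. The two parameters are not named, the VAS is undefined, and neither redaction nor PDF reading explains it. The consequence does not stand at the size claimed:

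- The argument treats the lists as closed, although the sentences around them are general and already supply a method.
- An outcome test is owed only if the parameter was measured after treatment, which the documents do not say.
- The mechanism check promises more than it delivers. A non-significant Mann-Whitney result is not evidence that the trunk was unchanged, and with no sample size or power in the documents there is no basis for reading it that way. The two explanations of a null result would remain hard to separate.
- The worry about late specification applies to every analysis in the SAP. If data had already been seen, naming a test at that stage would bring openness but not prespecification.

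**Conclusion.** No change to the plan is needed. This is a labelling gap of low severity between a short protocol and a short SAP, one that an analyst fills sensibly from the SAP's own general rules. It touches 2, 1 or 0 of six parameters, depending on what the VAS rates. Both parameters lie outside the stated aim, so following the plan as written leaves the comparisons on communication, daily living and quality of life where they were. No stated rule or number is wrong, and no bias can be computed from the documents.

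The conclusion rests on reading the Mann-Whitney and Chi-square sentences as general and on matching the other four parameters to CFCS, Viking, Katz and PedsQL by content. That match is partly inferred. It is least secure for communication, because CFCS may have been recorded only once. That uncertainty concerns the timing of CFCS and would not be resolved by adding tests for the trunk or gross motor function. Confidence is high that the two names are absent, and low to moderate about any consequence.

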**“Evaluation of The Effect of Neck and Trunk Stabilization Exercises on
Quality of Life and Communication in Children with Cerebral Palsy with
Oral Motor Problem”**

NCT04214080

03.12.2019

Statistical Analysis Plan

Descriptive statistics for continuous variables are expressed as mean (X), standard deviation (SD) values (Height, weight, body mass index (BMI), gender, etc); it is expressed as number (n) and percentage (%) for categorical variables.

In calculations, statistical significance level (α) was taken as 5% and values with $p < 0.05$ expressed statistical significance. "Statistical Package for Social Sciences" (SPSS 16) statistics program was used for calculations.

Non-parametric tests were applied since the continuous variables in the study were not normally distributed. Mann-Whitney U test was used to compare continuous variables according to Control and Study groups (Visual Analogue Scale, Viking Speech Scale, Communication Function Classification System, Katz scale, Sub-parameters of PedsQL). Wilcoxon test was used for intra groups comparisons (Visual Analogue Scale, Viking Speech Scale, Katz scale, Sub-parameters of PedsQL). In determining the relationship between categorical variables and groups, Chi-square test was performed (CP subtypes, Number of Medication, Types of Medications).

Spearman's Correlation Analysis was used to determine the relationship between groups of cases and other categorical and continuous variables (Visual Analogue Scale and Katz scale correlation analysis results with Communication Function Classification Systems).

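### Every p < 0.05 counts as significant across several between-group outcome tests, with no primary outcome, testing order, adjustment or exploratory label

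*SAP*

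**What the plan says.** The second paragraph of the SAP sets one rule for all tests: "statistical significance level (α) was taken as 5% and values with $p < 0.05$ expressed statistical significance".

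The third paragraph says that the "Mann-Whitney U test was used to compare continuous variables according to Control and Study groups", and lists "Visual Analogue Scale, Viking Speech Scale, Communication Function Classification System, Katz scale, Sub-parameters of PedsQL". It does not say how many PedsQL sub-parameters there are, or whether the scores compared are baseline, post-treatment or change. The same paragraph says that the "Wilcoxon test was used for intra groups comparisons (Visual Analogue Scale, Viking Speech Scale, Katz scale, Sub-parameters of PedsQL"). The Communication Function Classification System (CFCS) is absent from that second list. In the fourth paragraph CFCS is the variable against which two scales are correlated: "Visual Analogue Scale and Katz scale correlation analysis results with Communication Function Classification Systems".

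Neither document ranks the outcomes. The protocol's Objectives row gives the aim as the "effects of neck and trunk stabilization exercises on communication, activities of daily living and quality of life", which is three domains side by side. The SAP title names two of them: "Quality of Life and Communication in Children with Cerebral Palsy with". The protocol's Measured Parameters row lists six items without priority. Two of these, gross motor function and evaluation of the trunk in sitting, have no test named in the SAP. Neither document mentions an adjustment for multiple tests or describes the analysis as exploratory.

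**The concern.** With several outcomes, one threshold for each and no ranking, a single between-group p-value below 0.05 can be presented as the trial's finding. The 5% level describes the risk of error for one test only. The risk that at least one of the set is significant by chance is larger, and the plan does nothing to limit or disclose it.

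The within-group tests are no safeguard. The protocol's Design row gives oral motor rehabilitation and NDT-B to all children. Pre-post improvement in the study arm can therefore be real even if the added neck and trunk exercises contribute nothing. At stake is whether a claim that those exercises work rests on a controlled error rate.

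**Working it through.** The documents state no familywise error rate, sample size or power, so the only figure to reproduce is the per-test level. For one test, 1 - 0.95 = 5%, as the SAP says.

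**Inputs**
- Per-test level 0.05 (SAP, second paragraph). Sidedness is not stated; two-sided is assumed, so the critical value is 1.96 and the chance of a false result in favour of the study group is 2.5% per test.
- Number of outcome tests m, assumed to be 5 to 7. Five means the Visual Analogue Scale (VAS), Viking, Katz and two PedsQL sub-parameters, the fewest that the SAP's plural allows, with CFCS left out as a possible baseline classifier. Seven means those three scales, CFCS and three PedsQL sub-parameters, the three being inferred from the physical, psychosocial and school functions in the protocol's Measured Parameters.
- Correlation rho between test statistics, assumed to be 0 to 0.9.

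**Independent tests**
- Either direction, 1 - 0.95^m: m = 5 gives 22.6%, m = 6 gives 26.5%, m = 7 gives 30.2%.
- Favouring the study group, 1 - 0.975^m: 11.9%, 14.1% and 16.2%.

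**Correlated tests**

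Write each statistic as Z = sqrt(rho)·A + sqrt(1 - rho)·E, where A is a standard normal factor shared by all outcomes and E is specific to each. Then, integrating over A with the normal density:
- Either direction: 1 - ∫ [Φ((1.96 - sqrt(rho)·a)/sqrt(1 - rho)) - Φ((-1.96 - sqrt(rho)·a)/sqrt(1 - rho))]^m φ(a) da.
- Favouring the study group: the same, with only the first Φ term in the bracket.

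| m | Direction | rho 0 | 0.3 | 0.5 | 0.7 | 0.9 |
|---|---|---|---|---|---|---|
| 5 | either | 0.226 | 0.209 | 0.183 | 0.148 | 0.102 |
| 6 | either | 0.265 | 0.241 | 0.207 | 0.164 | 0.108 |
| 7 | either | 0.302 | 0.271 | 0.230 | 0.178 | 0.114 |
| 5 | study only | 0.119 | 0.105 | 0.091 | 0.074 | 0.051 |
| 6 | study only | 0.141 | 0.122 | 0.104 | 0.082 | 0.054 |
| 7 | study only | 0.162 | 0.137 | 0.115 | 0.089 | 0.057 |

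Every entry exceeds its single-test value of 0.05 or 0.025.

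**Ties and small arms**

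The normal model ignores both. Tie-corrected Mann-Whitney tests were simulated with 10 to 20 children per arm, five outcomes and four score levels; arm size and levels are assumptions.
- Levels equally likely: per-test error is 4.7-5.1%, and the either-direction error is 21.7-22.7% at latent correlation 0, 15.8-16.3% at 0.7 and 11.4-12.1% at 0.9.
- 85% of children at one level, 10 per arm: per-test error falls to about 2.3% and the either-direction error to 9-11% (latent correlation 0.7 to 0). By 20 per arm this reduction has gone.
- 90% at one level, 10 per arm: the either-direction error is about 4-5%, so there is no inflation.

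**Effect of Holm**
- First threshold 0.05/m: 0.0100 (m = 5), 0.0083 (m = 6), 0.0071 (m = 7).
- Familywise error for independent tests: 1 - (1 - 0.01)^5 = 0.049 for m = 5 and likewise about 0.049 for m = 7; lower if outcomes are positively correlated.
- Power: 80% at 0.05 implies a standardised effect of 1.960 + 0.842 = 2.802. At 0.0100 power is Φ(2.802 - 2.576) = 59%; at 0.0071 it is Φ(2.802 - 2.690) = 54%.

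**The case against.** The strongest reply is that the size is uncertain. The SAP gives no count of tests and no time point. If some Mann-Whitney tests are baseline checks, fewer are outcome tests; if both post-treatment and change scores are tested, there are more. So 5 to 7 is not a bound. The scales are measured in the same children and may well be correlated, which makes the zero-correlation column an upper case. With very small arms and scores piled up at one level, the tests become conservative and the inflation can vanish. All of this stands, and it limits the magnitude. It does not remove the gap: with only four outcome tests the independent-case figure is still 1 - 0.95^4 = 18.5%, and the setting without inflation requires an extreme score shape for every outcome, which nothing in the documents indicates.

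It can also be said that the aim is only to investigate effects and that no confirmatory hypothesis is stated. That is fair, and it is why an exploratory label is an equally sound remedy. But the plan carries no such label, and it does declare a significance rule.

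Two stronger readings are tempting. A reader might add gross motor function and trunk evaluation, reach nine tests and quote 37% (20% favouring the study group). The SAP names no test for those two parameters, so that count is not supported. A reader might also take "Non-parametric tests were applied since the continuous variables in the study were not normally distributed" as proof that the results were known when the SAP was written. It is one clause, with no distribution or normality test reported, and the protocol also uses the past tense. It suggests that the data may have been examined and shows no more than that.

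**Conclusion.** The concern holds, with a modest and uncertain size. The stated rule, applied to the between-group tests that the SAP names, lets the familywise error exceed 5%, and neither document limits or discloses this.

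For 5 to 7 outcome tests the chance of at least one false-positive difference in either direction is about 23-30% at correlation 0, 15-18% at 0.7 and 10-11% at 0.9. Favouring the study group, it is about 5-16% over the same range of correlations. These figures rest on an assumed number of tests, assumed correlation, two-sided testing and arms not so small, or scores not so concentrated, that the tests turn conservative. Within-group, chi-square and correlation tests are not counted.

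Confidence is high that the plan as supplied contains no primary outcome, order, adjustment or exploratory label, and lower for any single percentage. The point does not show that a given result is false or that an outcome was selected after the fact. It should be corrected before any between-group difference is claimed.

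**What to change.** State the single time point or change score used for each between-group outcome test, and report all of them. Then do one of the following; both are acceptable.

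- **(a) Adjust.** Apply Holm across every between-group outcome test that is run, with first threshold 0.0100 for 5 tests, 0.0083 for 6 and 0.0071 for 7. Add any further outcome that is compared, such as gross motor function or trunk evaluation. Keep baseline comparisons out of the family.
- **(b) Label.** Call all between-group results exploratory and make no significance claim from any single one.

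If a record that predates data review fixes one primary outcome, test it at 5% and treat the rest as secondary under Holm, claimed only if the primary is significant. Without such a record, do not choose a primary now, because the data may already have been examined.

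In every case, do not use the within-group Wilcoxon tests or the Spearman correlations as evidence that the added exercises work.

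Cost: SAP wording and, under (a), adjusted p-values; no new data. Option (a) loses power: an outcome with an assumed 80% power at 0.05 has about 59% (5 tests) to 54% (7 tests) at Holm's first threshold. Neither document gives a sample size, so the actual loss cannot be stated. Option (b) costs no power but gives up significance claims.
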